4.3. Parent R01: Studies and Results

4.3.1. Recruitment. Over the four-year recruitment period for the RCT (Aim 2), we enrolled and randomized 344 cases. This works out to 86 randomized cases per year. In the final year of recruitment for the randomized study, we recruited 88 cases. In the no-cost extension period, we recruited 115 AUD TAU only cases. Based on this, we estimate we can typically recruit about 2 cases per week in the proposed work.

4.3.2. Retention. Over the life of the study, our retention rate was 78.5% (i.e., attrition was 21.5%) at the four-month follow-up. Our retention procedures improved significantly as indicated by an 87% retention rate in the final year (i.e., attrition about 13%). Based on this, we estimate a 75% retention rate in the proposed work.

[figure not shown]

4.3.2. Findings. As can be seen in the graphs, the alcohol outcomes obtained in the CBT group were superior to the other groups in all cases. The effects between the randomized groups (CBT vs. PMRT) were small for categorical outcomes (any drinking: $X^2 = 4.05$, $p = .04$, $d = .26$; and any three consecutive days drinking: $X^2 = 3.71$, $p = .05$, $d = .25$) and medium for count outcomes (drinks per month: $X^2 = 25.63$, $p < .001$, $d = .68$; drinking days per month ($X^2 = 10.23$, $p = .001$, $d = .42$; and number of binge days per month: $X^2 = 13.46$, $p < .001$, $d = .48$

[the latter is not shown in the graph]). These results support the key study hypothesis from Aim 2 of

the parent R01; i.e., that CBT would produce superior alcohol outcomes relative to a randomized active treatment control. They further demonstrate that the active treatment control, PMRT, did not significantly improve alcohol outcomes relative to TAU controls; however, since the TAU group was not randomized, caution must be taken when interpreting the latter findings. Although patient's "principal" anxiety disorder did not moderate these study results, level of BL anxiety was the only significant moderator; i.e., lower BL anxiety was associated with reduced CBT effects.

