4.4. Parent R01: Significance

The practical significance of the parent R01 findings is in showing that augmenting AUD TAU with a six-session CBT reduces four-month relapse rates in those with co-occurring anxiety disorders by about one-quarter to one-third (i.e., TAU = 60%; PMRT = 53%; CBT = 41%). Although this eliminates only about half of the estimated increase in relapse risk attributable directly to the presence of a co-occurring anxiety disorder (e.g., Kushner et al., 2005), the large number of AUD treatment patients affected by co-occurring anxiety disorders (up to 50% of all cases) amplifies the potential benefit to the public health of these results. The aspects of the parent R01 findings with the greatest potential for theoretical significance are those pointing to the active ingredients by which the CBT improved AUD outcomes. The CBT and PMRT both produced a significant reduction in the percent of patients experiencing clinical-level anxiety at the post-treatment assessment, while only

the CBT demonstrated significantly better alcohol outcomes relative to TAU at the four-month assessment. These findings reinforce past studies showing that anxiety disorder treatment does not produce detectable improvements in alcohol outcomes (above). More importantly, these findings imply that the de-coupling therapy elements were the active ingredients that improved alcohol outcomes in the CBT group. This conclusion has the theoretical potential of informing modification to the CBT that would substantially improve its clinical effectiveness.

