6.0 STUDY PROCEDURES

6.1. Recruitment Strategy. Strategy: We will recruit individuals entering residential treatment for an alcohol use disorder at the Fairview Hospital Chemical Dependency program (Lodging Plus) for adults in Minneapolis. Participants will be recruited from the Consortium of Addiction Research (CAR) combined screening process, approved as IRB protocol #STUDY00005170. Complete details of the screening process can be found in the protocol for that study. Those who are eligible based on the CAR screening protocol will be invited to participate via the “1404S49427 Invite” and given a copy of the consent form. At the Baseline appointment they will have time to read the consent form and have their questions answered. In addition, they will watch a brief video of the study PI describing key elements of the study. If the staff person conducting the screening appointment is convinced the individual understands the consent form based on their answers to questions highlighting the key elements of participation, the individual will be offered the opportunity to sign the consent form. After signing the Consent Form, the baseline appointment will be completed and the appointments for the CBT therapy will be arranged.

Lodging Plus evaluates approximately 1000 chemically dependent patients per year, approximately 70% of whom are seeking treatment for alcohol dependence. Based on our experience in the parent R01 (see above), we should be able to recruit about two patients per week and a total of about 90-100 patients per year. Based on this, the target sample of 350 will be recruited in slightly less than 4 years. Our attrition rate over the entire life of the study was about 20% but was approximately 15% in the final year. (Note improvements in recruitment and retention over the course of the parent R01 reflects refined and improved methods based on our accumulating experience.) Based on the attrition estimate of 15%, we would have approximately 300 cases with four-month follow-up data, which will well power the study (see power estimates below).

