The principal power estimate focuses on categorical analyses since these will provide the most conservative power estimates and because we have somewhat more information available to estimate these outcomes for the Primary Aim study groups. (ES for continuous/count alcohol outcomes all demonstrated larger group effects than the categorical outcomes in the parent R01 [Kushner et al. 2013-a].) The best estimate for the categorical CBT-AR alcohol outcome comes from the PMRT group (also devoted exclusively to anxiety reduction) in the parent R01 (i.e., 53% relapse at four months). The parent R01 does not provide a point estimate for the CBT-DC group relapse rate but our prediction that the CBT-DC group will ameliorate all (or most) of the deleterious effect on recovery conferred by a co-occurring anxiety disorder allows us to place this estimate at 21%; i.e., the relapse rate at four months of an AUD treatment group with no co-occurring anxiety disorder (Kushner et al., 2005; also see Driessen et al., 2001 for similar estimates). These estimated results would represent a large effect size ($OR = 4.2$), which would require a sample of only 41 per group to identify an effect at an $\alpha = .05$ level with 80% power; however, a larger sample size would be required to identify other predicted effects with the same power. Further, we cannot be certain that our empirically- and theoretically-informed prediction that the CBT-DC will mitigate all/most of the risk for relapse conferred by co-occurring anxiety disorder is correct until the study is conducted. Therefore, we also calculated a minimum detectable ES showing that we could detect an OR as small as 2.3 with 80% power in the planned sample size using a two-tailed test and 0.05 alpha-level. Although we would be at a higher risk of missing effects even smaller than this, such negative findings would not constitute a meaningful Type II error because they would be of increasingly trivial clinical importance (e.g., Ferguson, 2009). **Therefore, the Primary Aim will be put to a meaningful and scientifically valid test under a wide range of clinically meaningful effect sizes.**

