7.6. Secondary Aim: To compare the CBT-DC and CBT-O groups on alcohol outcomes

The importance of this comparison includes confirming our hypothesis that 6 DC sessions are superior to 3 DC sessions in terms of alcohol outcomes (DC dose: high vs. low) while also ruling out the alternative hypothesis that, contrary to study predictions, de-coupling therapy elements can only exert a therapeutic effect on alcohol outcomes when combined with anxiety reduction elements ("synergy"). Regarding the affirmative dose prediction, we can estimate the effect of the CBT-O group to be the same as that of the CBT in the parent R01 (i.e., 41% relapse at 4 months), while keeping all other parameters, including the CBT-DC group effect estimate of 21% relapse, the same as outlined for the Primary Aim. These estimated results would represent a medium effect ($OR = 2.6$), which would require a sample of 94 per group to identify with 80% power an effect with $\alpha = 0.05$. (Again, we anticipate continuous/count tests will have greater power than categorical tests.) If, however, contrary to our study predictions, synergy between the therapy components is necessary,

then we would expect CBT-DC to resemble TAU only in outcome (61% relapse) with the CBT-O result still being the same as in the parent R01 (again, 41% relapse). This would provide roughly the same power to detect the unexpected synergy effect as there will be to detect the predicted dose effect; albeit, with opposite directional effects.

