7.8. Mechanism manipulation checks

The specific aims of this clinical research are to demonstrate the group differences in clinical outcomes predicted above. However, inferring that these differences were due the mechanisms targeted in the specific groups require demonstrating that the levels of change in the mechanisms as a result of treatment varied according to the group assignments as expected. This will be done using the anxiety reduction and de-coupling process measures described above taken at the pre-treatment baseline compared to the immediate post-treatment assessment. Given our sample size of 100 subjects per group, we will have 80% power to detect group differences of 0.40 SD units using a two-tailed test and a 0.05 alpha level. Since this minimally detectable ES is less than half of the natural variability of the measure and, therefore, on the low end of clinical and theoretical significance (e.g., Ferguson, 2009), our difficulty in detecting even smaller effects is not considered problematic.

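### Section 7.5 dismisses missed relapse effects below OR 2.3, yet the parent-trial relapse reductions that section 4.4 treats as practically significant are OR 1.62 and 2.16, and power at 1.62 is only 34% to 40%

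*Combined protocol and SAP*

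**What the plan says.** Section 7.5 bases its power statement on categorical relapse at four months. It expects 53% relapse with CBT-AR and 21% with CBT-DC, concedes that the 21% is uncertain, and offers a minimum detectable effect as the safeguard: "we could detect an OR as small as 2.3 with 80% power in the planned sample size using a two-tailed test and 0.05 alpha-level". Of effects below that size it says that "such negative findings would not constitute a meaningful Type II error because they would be of increasingly trivial clinical importance", citing a general effect-size reference. A conclusion in bold follows: the Primary Aim will be validly tested over a wide range of clinically meaningful effects.

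Section 4.4 describes the practical significance of the parent trial. Adding the six-session CBT to usual treatment "reduces four-month relapse rates in those with co-occurring anxiety disorders by about one-quarter to one-third", with rates of 60% (usual treatment), 53% (relaxation control, PMRT) and 41% (CBT). It adds that the number of patients affected amplifies the public health benefit.

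Two sample sizes can be derived. Section 7.8 has "Given our sample size of 100 subjects per group", and section 6.1 agrees: "Based on the attrition estimate of 15%, we would have approximately 300 cases with four-month follow-up data". Section 4.3, on retention, says "we estimate a 75% retention rate in the proposed work".

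**The concern.** A minimum detectable effect is a property of the sample size. It does not show that smaller effects are unimportant; that needs a clinical argument. Here the documents' own clinical argument points the other way, because the reductions valued in section 4.4 fall on the side of the line that section 7.5 sets aside.

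What is at stake is how a non-significant relapse comparison would be read. With the sentence in place, a reader could take such a result as showing that nothing worthwhile was missed, although the design would miss a difference the size of the parent trial's randomized contrast more often than it found one.

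**Working it through.** **Inputs.** Two-sided alpha 0.05 and detectable OR 2.3 (section 7.5); 53% for CBT-AR (section 7.5); parent rates 60%, 53% and 41% (section 4.4); 100 per group (section 7.8); 75% retention (section 4.3), so 350 × 0.75 / 3 = 87 per group. Equal allocation is inferred from the 100 per group.

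**Formula.** Power = Φ{[d − 1.96·√(2p̄(1−p̄)/n)] / √([p1(1−p1)+p2(1−p2)]/n)}, where d = |p1−p2| and p̄ is the mean of p1 and p2. The continuity-corrected version replaces d by d − 1/n.

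**1. The plan's own figure.** Solving for 80% power from 53% at n = 100 gives p2 = 33.5%, OR 2.24. The continuity-corrected sample-size formula gives 32.5%, OR 2.34. The stated 2.3 is reproduced. The corrected formula also gives 41 per group for 53% v 21% (stated 41) and 93 for 41% v 21% (stated 94).

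**2. What OR 2.3 means.** The odds at 53% are 0.53/0.47 = 1.128. Then 1.128/2.3 = 0.490, and 0.490/1.490 = 32.9%. The sentence therefore covers true reductions of up to about 20 percentage points.

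**3. The parent contrasts on the same scale.** The odds at 41% are 0.41/0.59 = 0.695.
- Randomized, 53% v 41%: 1.128/0.695 = 1.62; relative reduction 1 − 0.41/0.53 = 23%.
- Non-randomized, 60% v 41%: 1.500/0.695 = 2.16; relative reduction 1 − 0.41/0.60 = 32%.

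These two reductions match the range given in section 4.4, and both ORs are below 2.3.

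**4. Power for 53% v 41%.** At n = 100, d = 0.12 and p̄ = 0.47. The null standard error is √(0.4982/100) = 0.0706 and the alternative standard error is √(0.4910/100) = 0.0701. Then (0.12 − 0.1383)/0.0701 = −0.26, so power is 40%. With d − 1/n = 0.11, the value is −0.40 and power is 34%.

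| n per group | Basis | Power (continuity-corrected) |
|---|---|---|
| 87 | 75% retention | 35% (30%) |
| 100 | planned | 40% (34%) |
| 117 | all 350 followed | 45% (40%) |

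Exact enumeration at n = 100 gives 42% for the Pearson chi-square test and 36% for Fisher's test. Power of 80% would need 271 per group (287 corrected). The abstract gives the control rate as 54%; that makes the OR 1.69 and power at 100 per group 45% (40%).

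**5. Power for 60% v 41%.** At n = 100 it is 77% (72% corrected).

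**6. How such a result would look.** Suppose the trial observed exactly 53/100 v 41/100. The standard error of the log OR is √(1/53+1/47+1/41+1/59) = 0.285, so the 95% CI is exp(0.484 ± 0.559), or 0.93 to 2.84. That is non-significant, yet compatible with effects well above OR 2.3.

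**The case against.** **The low power is not a property of the whole trial.** This stands. Section 7.5 also makes drinking severity primary and says the categorical analysis was chosen as the conservative one. The parent effect on drinking days per month was d = .42. If that is read as a standardized mean difference (an approximation for count data), power at 100 per group is Φ(0.42·√50 − 1.96) = 84%. A reader might infer that the design would usually miss any parent-sized effect. The documents support that only for relapse status.

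**The parent contrast is not the primary contrast.** This also stands. Original CBT v relaxation corresponds most directly to CBT-O v CBT-AR, the Tertiary Aim. CBT-DC v CBT-AR compares six de-coupling sessions with none and could show a larger effect. OR 1.62 is a benchmark with randomized evidence behind it, not a prediction for the Primary Aim.

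**Section 4.4 describes a range, and section 4.3 calls the categorical effect small.** Both are true. OR 1.62 is the lower end of the range, but the upper end is also below 2.3, and small is not the same as trivial.

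**Section 7.5 describes a gradient and cites a source.** The wording is graded, but it still denies a meaningful error anywhere below 2.3. A general reference does not settle a conflict with the plan's own account of what matters.

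**The synergy scenario in section 7.6 might look like a further contradiction.** At 61% v 41% it is OR 2.25, nominally below 2.3. Its power at 100 per group is 81% (77% corrected), so it sits at the detectable limit and the gap is one of rounding and formula. It adds nothing to the point.

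**Conclusion.** For categorical relapse, the claim that effects below OR 2.3 are not worth detecting conflicts with section 4.4, where reductions of OR 1.62 and 2.16 carry the parent trial's practical significance. Power for the randomized one is 34% to 40% at 100 per group and 30% to 35% at 87. The chance of missing a true difference of that size is therefore about 60% to 70%. This rests on a 53% comparator rate, equal groups, a two-sided 0.05 test and no covariate adjustment.

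A reader might go further and say that the plan commits the trial to interpreting a null result as no effect. It does not: the sentence is part of a power rationale, and section 7.5 sets no rule for reading a non-significant result. Nor does any document name OR 1.62 as a minimum important difference. The calculation behind 2.3 is sound; the fault lies in the clinical interpretation attached to it.

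**What to change.** In section 7.5:

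- Delete the sentence denying a meaningful Type II error, and limit the bold conclusion to relapse effects of about OR 2.3 or larger.
- Beside the minimum detectable OR, state the power for OR 1.62 (53% v 41%): 40%, or 34% with continuity correction, at 100 per group; 35% (30%) if retention is 75%.
- State that a non-significant relapse comparison will be reported with its 95% CI, and will not be read as absence of a clinically meaningful effect when that interval includes effects of the parent trial's size.

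A fixed rule that calls a result inconclusive unless the interval excludes OR 1.62 is not recommended. The documents set no such margin. With 53% relapse in both groups of 100, an observed OR of 1.0 already has an upper limit of exp(1.96 × 0.283) = 1.74, and about 60% of results under a true null would fail the rule.

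The cost is wording only: no extra patients, visits or tests. The downside is that the stated sensitivity looks less favourable.

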7.6. Secondary Aim: To compare the CBT-DC and CBT-O groups on alcohol outcomes

The importance of this comparison includes confirming our hypothesis that 6 DC sessions are superior to 3 DC sessions in terms of alcohol outcomes (DC dose: high vs. low) while also ruling out the alternative hypothesis that, contrary to study predictions, de-coupling therapy elements can only exert a therapeutic effect on alcohol outcomes when combined with anxiety reduction elements ("synergy"). Regarding the affirmative dose prediction, we can estimate the effect of the CBT-O group to be the same as that of the CBT in the parent R01 (i.e., 41% relapse at 4 months), while keeping all other parameters, including the CBT-DC group effect estimate of 21% relapse, the same as outlined for the Primary Aim. These estimated results would represent a medium effect ($OR = 2.6$), which would require a sample of 94 per group to identify with 80% power an effect with $\alpha = 0.05$. (Again, we anticipate continuous/count tests will have greater power than categorical tests.) If, however, contrary to our study predictions, synergy between the therapy components is necessary,

then we would expect CBT-DC to resemble TAU only in outcome (61% relapse) with the CBT-O result still being the same as in the parent R01 (again, 41% relapse). This would provide roughly the same power to detect the unexpected synergy effect as there will be to detect the predicted dose effect; albeit, with opposite directional effects.

7.7. Tertiary Aim: To compare the CBT-O and CBT-AR groups on alcohol outcomes

The importance of this comparison includes confirming our hypothesis that 3 DC sessions are superior to zero DC sessions (DC dose: low vs. none) in terms of alcohol outcomes, while also exploring the alternative hypothesis that, contrary to study predictions, a high vs. a low dose of anxiety reduction therapy (i.e., 6 vs. 3 sessions) is needed to improve alcohol outcomes. Regarding the former, just as the CBT-DC group has three more DC sessions than the CBT-O group (6 vs. 3), the CBT-O group has three more DC sessions than the CBT-AR group (3 vs. zero). Regarding the affirmative dose prediction, we anticipate that the size of this effect will be the same as the size of the effect for the Secondary Aim: i.e., requiring 94 cases per group to obtain 80% power to detect an effect with alpha set at the .05 level. However, this dose-based prediction, if confirmed, will be somewhat more ambiguous than in the Secondary Aim because it could result either from the greater DC dose (as predicted) or DS-AR synergy. (In the Secondary Aim, by contrast, the group effects for dose and synergy should be in the opposite direction.) Alternatively, if the CBT-AR group is superior to the CBT-O group, this would suggest unambiguously that a higher dose of anxiety reduction is more important to improving alcohol outcomes than is a lower dose, even when combined with a low dose of de-coupling therapy.

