7.5. Primary Aim: To compare the CBT-DC and CBT-AR groups on alcohol outcomes

We predict that the CBT-DC group will have superior alcohol outcomes compared to the CBT-AR group. The primary intention to treat (ITT) population will include all patients randomized. The per-protocol (PP) population will include patients who completed at least four of six (66%) of the therapy sessions with CBT-O patients not missing any more than one of the three AR or DC content sessions. Hypotheses based on the vicious cycle model and parent R01 findings suggest that without alcohol-anxiety de-coupling therapy, drinking relapse is more likely to occur and more severe when it does occur. Therefore, we consider as primary outcomes both categorical relapse status (yes vs. no) and continuously measurement of relapse severity (percent/number days drinking and drinks per drinking day). Secondary alcohol outcomes tested include categorical status on: a) alcohol dependence (yes vs. no) and hazardous drinking (yes vs. no). Follow-up assessments occur 1-, 4- and 8-months following the conclusion of the study therapy and are keyed to the time since the last assessment. To align study findings with the parent R01, the primary assessment point will be the 4-month FU. However, hypotheses will also be tested across all time points to establish temporal patterns of group effects. We test the hypotheses using mixed effects models if data residuals are

normally distributed and generalized estimating equations (GEE) if the data are non-normally distributed (Gueorguieva, & Krystal, 2004; Liang & Zeger, 1986). Both are flexible regression methods for incomplete repeated measures data and allow continuous and categorical covariates, fixed and time-dependent covariates, and a specification of unstructured as well as structured covariance matrix. Categorical outcomes will be evaluated using chi-square tests of proportions and logistic regression, with statistical significance criterion also set at $p < 0.05$. Zero-inflated negative binomial analyses will be used to contrast the study groups on count variables if warranted by a high percentage of zero alcohol use days over the follow-up (e.g., Agresti, 2002).

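### Section 7.7's 94 per group for 80% power (CBT-O vs CBT-AR) contradicts the plan's own relapse estimates of 53% and 41%, which give about 34–42% power at 100 per group

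*Combined protocol and SAP*

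**What the plan says.** Three sections of the combined protocol and SAP set four-month relapse rates or rely on them.

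- **Section 7.5 (Primary Aim)** sets CBT-AR: "The best estimate for the categorical CBT-AR alcohol outcome comes from the PMRT group", which it describes as "also devoted exclusively to anxiety reduction) in the parent R01 (i.e., 53% relapse at four months". CBT-DC is set at 21%, giving OR 4.2 and 41 per group. The section adds that "we could detect an OR as small as 2.3 with 80% power in the planned sample size", two-tailed at 0.05.
- **Section 7.6 (Secondary Aim)** sets CBT-O to be the "same as that of the CBT in the parent R01 (i.e., 41% relapse at 4 months". Against 21% for CBT-DC this gives OR 2.6 and 94 per group.
- **Section 7.7 (Tertiary Aim)** compares CBT-O with CBT-AR but uses neither arm's rate. It notes that the two arms differ by three de-coupling sessions, as CBT-DC and CBT-O do, and concludes that "we anticipate that the size of this effect will be the same as the size of the effect for the Secondary Aim", "requiring 94 cases per group to obtain 80% power to detect an effect with alpha set at the .05 level".

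Relapse is a primary outcome but not the only one. Section 7.5 says "we consider as primary outcomes both categorical relapse status (yes vs. no) and continuously measurement of relapse severity", the latter being days drinking and drinks per drinking day. Its principal power estimate rests on the categorical outcome.

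**The concern.** With three arms, two of the pairwise effects fix the third. Sections 7.5 and 7.6 put CBT-AR, CBT-O and CBT-DC at 53%, 41% and 21%. That leaves 12 points between CBT-AR and CBT-O, whereas section 7.7 plans on the 20-point effect between CBT-O and CBT-DC. The three sections cannot all hold.

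A reader of section 7.7 would believe that the relapse comparison has 80% power. The section interprets superiority in either direction but does not say how a non-significant result will be read. Section 7.5 does comment on negative findings: effects below OR 2.3 are treated as increasingly trivial clinically, so missing them is not a meaningful Type II error. That remark is made for the Primary Aim and is not extended to section 7.7. If it were, the parent trial's own 53% vs 41% difference would count as near trivial, although section 4.4 presents it as part of that trial's practical significance. With power overstated, a null relapse result could be taken as evidence against a de-coupling dose effect when the comparison was unlikely to detect the effect the plan predicts.

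**Working it through.** **Inputs.** CBT-AR 53% (section 7.5); CBT-O 41% and CBT-DC 21% (section 7.6); two-sided 0.05 (section 7.5); 80% power and 94 per group (section 7.7); 100 analysed per group (section 7.8; section 6.1 expects about 300 of 350 after 15% attrition).

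**Formulas.** With d = p1 − p2 and p̄ the mean of the two rates:

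- n = [1.960·√(2p̄(1−p̄)) + 0.842·√(p1(1−p1) + p2(1−p2))]² / d²
- continuity-corrected n′ = (n/4)·[1 + √(1 + 4/(n·d))]²

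**Step 1: reproduce the plan's figures.**

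| Comparison | OR | n uncorrected | n corrected | Plan |
|---|---|---|---|---|
| 53% vs 21% (Primary) | 4.24 | 34.5 | 40.5 | 41 |
| 41% vs 21% (Secondary) | 2.61 | 82.8 | 92.5 | 94 |

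The corrected formula matches the first figure and comes within two of the second, so it is close to the plan's method. The 94 comes from 41% vs 21%.

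**Step 2: apply the same method to the arms in section 7.7.** For 53% vs 41%, d = 0.12 and p̄ = 0.47.

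- OR = (0.53/0.47)/(0.41/0.59) = 1.62
- n = [1.960·√0.4982 + 0.842·√0.4910]² / 0.0144 = 270.4, so 271 per group
- n′ = 286.8, so 287 per group

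**Step 3: power at the planned size.** At 100 per group the null standard error is √(0.4982/100) = 0.0706 and the alternative is √(0.4910/100) = 0.0701.

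- Uncorrected: Φ[(0.12 − 1.960·0.0706)/0.0701] = Φ(−0.26) = 0.40
- Corrected: Φ[(0.12 − 0.01 − 1.960·0.0706)/0.0701] = Φ(−0.40) = 0.34
- Exact (both binomials summed over the Pearson chi-square rejection region): 0.42

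| n per group | Corrected | Uncorrected | Exact |
|---|---|---|---|
| 87 (75% retention, section 4.3: 350 × 0.75 / 3 = 87.5) | 0.30 | 0.35 | 0.38 |
| 94 | 0.32 | 0.38 | 0.37 |
| 100 | 0.34 | 0.40 | 0.42 |
| 117 (all 350 analysed) | 0.40 | 0.45 | 0.48 |

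If the rates occur exactly as planned at 100 per group, the difference is 12 points with a 95% CI of ±1.96 × 0.0701 = ±13.7 points, that is −1.7 to 25.7.

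**Step 4: consistency with the rest of the plan.**

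- The stated Primary and Secondary odds ratios already imply the Tertiary one: 4.24 / 2.61 = 1.62.
- From 41% at 100 per group, the minimum detectable OR is 2.22 uncorrected or 2.32 corrected. This agrees with the plan's 2.3, and 1.62 lies below it.
- For section 7.7's equality to hold, CBT-AR would have to relapse at 61% (same 20-point gap) or about 64% (same OR). The same-OR case would make the Primary OR 2.61² ≈ 6.8 instead of 4.2.
- Section 4.3 reports the parent trial's CBT vs PMRT effect on any drinking as d = .26. OR 1.62 converts to d = ln(1.62)·√3/π ≈ 0.27.

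**Step 5: sensitivity.** The abstract gives the parent control's relapse as 54%. With that rate, 80% power needs 231 to 246 per group, and power at 100 is 0.40–0.47.

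**The case against.** The strongest reply is that 53% is only a proxy. CBT-AR had not been run; the figure comes from a relaxation control that did not significantly improve alcohol outcomes over treatment as usual. Section 7.6 puts treatment as usual alone at 61%. If CBT-AR relapsed at 61%, power at 100 per group would be 0.77–0.83, close to the claim. The uncertainty is real, but section 7.7 does not invoke 61%, section 7.5 treats 53% as its best estimate for this arm, and using 61% here would contradict the Primary Aim calculation.

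Section 7.7 also says openly that it anticipates an equal effect and gives a reason. But equal session increments do not override arm-specific rates given in the two preceding sections, and no reconciliation is offered.

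The count outcomes are also primary, and the plan expects more power from them. This stands as a limit on the claim. If the parent trial's d = .42 for drinking days held, a t-test approximation gives 0.84 at 100 per group and 0.79 at 87. The Tertiary Aim as a whole is therefore not shown to be underpowered. Section 7.7 gives no such calculation, however, and the planned models for those outcomes are mixed effects, GEE or zero-inflated negative binomial.

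Finally, this is the third-ranked aim, which limits the consequences but does not make the stated power correct.

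**Conclusion.** The concern holds. On the plan's own rates, the relapse comparison of CBT-O with CBT-AR has about 34–42% power at 100 per group, not 80%, and would need 271 to 287 per group instead of 94, roughly three times as many. The 94 is nearly exact for 41% vs 21%; the error is its transfer to a pair of arms for which the plan gives different rates. The conclusion rests on 53% and 41%, a two-sided 0.05 test and categorical relapse at four months. Neither analysing all 350 (at most 0.48) nor using the abstract's 54% (at most 0.47 at 100 per group) brings power near 80%. It should be corrected. It does not affect the Primary Aim calculation, and it makes no claim about the count outcomes.

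**What to change.** Replace the power sentence in section 7.7 with text such as:

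> For categorical relapse, taking 53% for CBT-AR and 41% for CBT-O (OR 1.6), 80% power would require about 271–287 per group; 100 per group gives about 34–42%. Power for the count and continuous primary outcomes may be higher. The relapse difference will be reported with a 95% confidence interval, and a non-significant result will not be interpreted as absence of a dose effect.

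The 84% for drinking days may be added if it is labelled as a t-test approximation conditional on d = .42; it is optional. If the sponsor instead believes that CBT-AR will relapse at 61% or more, section 7.7 should state and justify that rate and reconcile it with the 53% in section 7.5.

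The cost is wording in one place. Enrolment and section 7.5 are unchanged under the proposed text; the only loss is a less favourable power statement for this comparison.
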